## 14 Appendix 2: Japanese Package Insert for Dovobet® ointment

Revised in Feb/2018 (2nd edition)  
Prepared in Sep/2014

Japan standard commodity classification number
872699

Powerful drug            **Therapeutic drug for psoriasis vulgaris**

Prescription drug note    **Dovobet® Ointment**

**Calcipotriol hydrate/Betamethasone Dipropionate Combination**

**Dovobet® Ointment**

Approval number	22600AMX00752
NHI price listing	September 2014
Initial marketing in Japan	September 2014
International birth date	March 2001

Storage: Stored at room temperature

Expiration date: Indicated on the carton, etc. (Two year after being manufactured)

Note) Cautions – Use only under description as directed by a physician

### [Contraindications (This medication contraindicated in the following patients.)]

1. Patients who have a history of hypersensitivity to any ingredients of this product
2. Patients with bacterial, fungal, spirochetal or viral skin infection or with animal skin disease (scabies, crab lice, etc.) [these diseases may worsen.]
3. Ulcers (excluding Behcet's disease), deep burns of second or severer grade, and frostbite [skin regeneration may be suppressed, resulting in delayed healing.]

### [Description]

Ingredients	Active Ingredients /amount (per 1 g)	Calcipotriol hydrate 52.2µg (equivalent to calcipotriol 50.0µg), betamethasone dipropionate 0.643mg
	Excipients	All-rac-α-tocopherol Liquid paraffin White soft paraffin Polyoxypropylene stearyl ether
Appearance/description		Yellowish white to yellow ointment

### [Indication]

Psoriasis vulgaris

**[Dosage and Administration]**

Apply adequate amount of Dovobet® ointment to the affected area once daily.

<Precautions regarding dosage and administration>

The maximum weekly dose should not exceed 90 g.

**[Precautions]****1 Careful administration (This medication should be carefully administered to the following patients.)**

1. Patients with hypercalcemia and those who are at risk for hypercalcemia [serum calcium level may be increased more.]
2. Patients with renal dysfunction [the administration of this product may increase serum calcium levels.]

**2. Important precautions**

- (1) This product is a combination drug containing calcipotriol hydrate and betamethasone dipropionate. Adverse drug reactions caused by the use of calcipotriol or betamethasone may occur, therefore appropriate use of this drug should be considered.
- (2) This product is an active vitamin D3 containing preparation. This medication may increase serum calcium level. Since hypercalcemia may induce a decrease in renal function, patients should be monitored for serum calcium level and renal function (e.g. creatinine and BUN) periodically (once at 2 - 4 weeks after the start of administration of the product and when deemed necessary thereafter). If any abnormality is observed in these values, the administration of the product should be discontinued until normal calcium levels are restored.
- (3) Efficacy and safety when this product is applied more than 4 weeks have not been established [See section "Clinical results"]. The clinical course should be closely observed during treatment. Use of this product should not be continued aimlessly.
- (4) Overdosage of the product may induce hypercalcemia. Hypercalcemia may also occur in patients using the product for eruption covering a large area of the body or in patients with deteriorated skin barrier function which may accelerate percutaneous absorption of the drug. If any abnormality suggestive of hypercalcemia is observed, the administration of the product should be discontinued immediately and the patient should be followed up by observing biochemical parameters such as serum and urinary calcium levels [See section 8. "Overdosage" for signs/symptoms of hypercalcemia].
- (5) Local adverse reactions, such as skin atrophy, steroid flush, etc. may occur. Therefore, careful consideration should be given particularly when this medication is used for

eruptions on the neck, genitals and skin folds.

- (6) This product contains a corticosteroid and concurrent treatment at the same treatment area with other steroids must be avoided. When use in large doses or for prolonged periods over a large surface area [particularly under the occlusive dressing technique (ODT)], symptoms such as those that are likely to occur in systemic administration of adrenocortical steroids may occur. Therefore, prolonged use in large doses or ODT should be avoided.
- (7) This medication contains calcipotriol. The safety of the product, when applied by the occlusive dressing technique (ODT), has not been established (incidence of skin irritation is higher in ODT than plain application. ODT may enhance percutaneous absorption of the drug, and may increase the incidence of systemic adverse effects as compared with plain application).

### 3. Drug interactions

Precautions for coadministration (Dovobet® ointment should be administered with care when coadministered with the following drugs.)

Drugs	Signs, symptoms, and treatment	Mechanism and risk factors
Vitamin D and its analogues Alfacalcidol, calcitriol, tacalcitol, maxacalcitol, etc.	Hypercalcemia may be induced.	Additive effect
Cyclosporin		Increase of serum calcium level may easily be induced due to renal impairment by cyclosporine.

### 4. Adverse drug reactions

In clinical studies conducted in Japan before approval of Ointment and before approval of Gel, 17 adverse drug reactions were reported in 17 of the 445 treated patients (3.8%).

Those adverse drug reactions were folliculitis in 5 patients, anaemia and glucose urine present in 2 patients each, and leukocytosis, oedema peripheral, hepatic function abnormal, herpes simplex, rash pustular, contusion, psoriasis aggravated and skin depigmentation in 1 patient each.

- (1) Clinically significant adverse drug reactions
- 1) Hypercalcemia (information from Package Insert of calcipotriol, frequency unknown): Hypercalcemia and clinical symptoms that are considered to be due to hypercalcemia (malaise, feelings of weakness, anorexia, vomiting, abdominal pain and muscle weakness, etc.) may appear. If any abnormalities are noted, use of this medication should be discontinued, and biochemical tests including serum calcium and urine calcium should be conducted. If necessary, actions such as intravenous fluids should be taken.

2) Acute kidney injury (information from Package Insert of calcipotriol, frequency unknown): Acute kidney injury accompanied by serum calcium increased may appear. If any abnormalities such as serum creatinine increased and BUN increased are noted, use of this medication should be discontinued, and an appropriate action should be taken.

(2) Other adverse drug reactions

If the following adverse drug reactions are observed, appropriate measures should be taken.

	≥ 1%	< 1%	Unknown*
Hypersensitivity note1			Erythema/redness,
Skin note2		Psoriasis aggravated	Itch, pruritus, burning sensation, pricking skin feeling, skin irritation, dermatitis, Ichthyosis-like dermal changes, skin dryness, skin erosion, contact dermatitis, exfoliation, eruption, swelling
Skin infection note3	Folliculitis		Bacterial infection (infectious impetigo, furuncle, etc.), dermatomycosis (candidiasis, tinea, etc.), viral infection
Other skin symptoms note4		Rash pustular, Skin depigmentation	Skin pigmentation, pustular psoriasis, acneform eruption, rosacea-like dermatitis, steroid skin (skin atrophy, telangiectasis and purpura), hypertrichosis,
Hepatic		Hepatic function abnormal	Increased AST(GOT), increased ALT(GPT) increased $\gamma$ -GTP, increased LDH, increased ALP, increased total bilirubin
Renal			Increased BUN, increased serum creatinine, increased urinary creatinine
Hematologic		Leukocytosis, anaemia	Leukopenia, leukocytosis, decreased haemoglobin, lymphopenia, monocytosis, neutropenia
Infection		Herpes simplex	
Function of pituitary adrenocortical system			Suppress the function of the pituitary adrenocortical system note5
Others		Oedema peripheral, Contusion, glucose urine present	Increased urinary calcium, increased serum calcium, increased serum phosphorus, decreased urinary phosphorus, increased serum $1\alpha,25(\text{OH})_2\text{D}_3$ , decreased serum phosphorus, decreased serum $1\alpha,25(\text{OH})_2\text{D}_3$ , rebound effect

The incidence is the sum of adverse drug reactions observed in clinical studies of Dovobet Ointment and Dovobet Gel conducted in Japan.

\* ADRs from overseas studies, calcipotriol preparation or betamethasone dipropionate preparation, therefore frequency is unknown in Japanese patients.

note 1: Discontinue application of this medicine if any symptom is observed.

note 2: Discontinue application of this medicine if the adverse drug reactions occur severely.

note 3: When any of these symptoms are observed, this medication should be used in combination with a suitable antibacterial drug or antifungal drug, and if the symptom does not disappear promptly, the administration of this medication should be discontinued. [Such symptoms are liable to occur when used under the occlusive dressing technique (ODT).]

note 4: When any of these symptoms occur after long term application, the use of this medication should be avoided, and changed over to some other drug(s) not containing adrenocortical steroid.

note 5: Event due to application in large doses, usage for prolonged periods over a large surface area or used under the occlusive dressing technique (ODT) in application of betamethasone dipropionate. Since acute adrenocortical insufficiency may occur by the discontinuation of this medication, the dose should be gradually reduced under close observation of the patient's conditions when the administration of this medication is discontinued.

## 5. Use in the elderly

In general, elderly patients have a deterioration of physiological functions. Therefore, attention should be given to overuse in elderly patients.

## 6. Use during pregnancy, delivery and lactation

### (1) Pregnant women, etc.:

It is desirable not to use this medication in pregnant women or women who may be pregnant [safety in application during pregnancy has not been established. It has been reported that calcipotriol is transferred to fetuses via the placenta in an animal experiment (rats). It has been reported that betamethasone has teratogenic action in animal studies (mice, rats, rabbits)] .

### (2) Nursing women:

It is desirable to avoid the use of this medication in nursing women. If this medication is used in nursing women by necessity, patients should be instructed to refrain from breastfeeding [It has been reported that calcipotriol is excreted in milk in an animal experiment (rats)] .

## 7. Use in children, etc.

Safety in low birth weight infants, neonates, nursing infants, infants and children has not been established (there is no experience).

## 8. Overdosage

**Signs and symptoms:** The major symptoms of hypercalcemia include malaise, feelings of weakness, anorexia, nausea, vomiting, enlarged feeling of abdomen, abdominal pain, headache, dizziness, muscle pain and muscle weakness, etc.

[See Section (2), (4) of “Important precautions”.]

**Treatment:** Use of this medication should be discontinued immediately. Biochemical tests including serum calcium and urine calcium should be conducted. If necessary, treatments such as intravenous fluids should be taken.

[See Section (2), (4) of “Important precautions”.]

## 9. Precautions concerning use

### (1) Application sites:

- 1) This medication should not be applied to the face.
- 2) This medication should not be used for ophthalmic application.
- 3) This medication should not be applied to any sites except for the affected areas.

(2) At the time of use: Be careful not to touch the face and wound sites with hands exposed to this medication.

### (3) After use:

- 1) Wash your hands thoroughly after using this medication to avoid the transference

of this medication to the face, etc.

- 2) It is not recommended to take a shower or bath immediately after application of this medication.
- (4) At the time of delivery of this medication: Special attentions should be given to the storage of this medication to prevent inappropriate use (oral use, etc.). Especially, this medication should be kept out of reach of children. If a patient takes this medication orally by mistake, the patient should be instructed to take appropriate action such as consulting a medical institution because systemic adverse drug reactions such as hypercalcemia may occur.  
[See Section “Overdosage”.]

## 10. Other precautions

- (1) It has been reported that in a study using male and female albino hairless mice to which light (xenon lamp) was irradiated for 40 weeks and calcipotriol solution was applied, the irradiation time required for inducing skin tumor was shortened significantly in males. However, in a study in which only the drug solution was applied to mice, no skin tumor was induced.
- (2) It has been reported that erythrodermic psoriasis, pustular psoriasis, etc. occurred during or after discontinuation of application of this medicine.

## [Pharmacokinetics]

In the study where this product once daily was applied to 13 Japanese subjects with severe psoriasis vulgaris, plasma concentration of calcipotriol, and betamethasone dipropionate were BLQ (below 50.0 pg/mL and 30.0 pg/mL, respectively) in almost all subjects. The ranges of  $C_{max}$  and  $AUC_{last}$  for the two subjects with quantitative concentration of calcipotriol were 56.1 to 159 pg/mL and 28.1 to 311 h•pg/mL, respectively. The  $C_{max}$  and  $AUC_{last}$  for the one subject with quantitative concentration of betamethasone dipropionate were 39.6 pg/mL and 41.24 h•pg/mL, respectively.

Plasma concentration of main metabolite of calcipotriol was quantified in 1 to 3 subjects at each time point. The ranges  $C_{max}$  and  $AUC_{last}$  for those subjects were 26.4 to 151 pg/mL and 27.9 to 736 h•pg/mL, respectively. Plasma concentration of main metabolite of betamethasone dipropionate was quantified in 5 to 11 subjects at each time point. The ranges  $C_{max}$  and  $AUC_{last}$  for those subjects were 30.3 to 910 pg/mL and 15.91 to 4732 h•pg/mL, respectively.

## [Clinical results]

The clinical efficacy of this product once daily application for 4 weeks was confirmed in the double-blind comparative study with the calcipotriol (twice daily application) and betamethasone dipropionate (once daily application) in Japanese psoriasis vulgaris patients. Mean percentage change in m-PASI from baseline is shown in the following table. Once daily application of this medication for 4 weeks showed the excellent therapeutic effect compared with comparators.

	Calcipotriol hydrate/ Betamethasone dipropionate  (n=226)	Calcipotriol  (n=227)	Betamethasone dipropionate  (n=223)
Mean percentage change in m-PASI from baseline to Week 4 (±SD)	-64.3% (24.7)	-50.5% (32.1)	-53.6% (26.4)

(Calcipotriol hydrate/Betamethasone dipropionate vs Calcipotriol, Calcipotriol hydrate/Betamethasone dipropionate vs Betamethasone dipropionate,  $p < 0.0001$  for all comparison)

## [Pharmacology]

### 1. Action of mechanism

Calcipotriol binds to the vitamin D receptor, and it has been reported that calcipotriol inhibits cell proliferation, regulates cell cycles and induces differentiation in various cell types, regulate abnormal expression of proinflammatory cytokines and control anti-microbial peptide expression.

Betamethasone dipropionate acts by binding to and activating the glucocorticoid receptor in the target cells. After binding to the receptors, corticosteroids including betamethasone dipropionate inhibit the production of inflammatory cytokine as well as the expression of other types of inflammatory mediators including intercellular adhesion molecule-1, the enzymes phospholipase A2, cyclooxygenase type 2 and inducible nitric oxide synthase. Inhibition of the expression of these enzymes results in the attenuated production of inflammatory mediators.

### 2. Effect of concomitant use

Treatment with the calcipotriol/betamethasone dipropionate combination significantly inhibited the differentiation and activity of human type 1 helper T (Th1) cell / IL-17 expressing helper T (Th17) cell. The inhibitory effect of treatment with the combination on differentiation and activity of Th1/Th17 cells was greater than either that of calcipotriol alone or betamethasone dipropionate alone.

[figure not shown]
**[Physicochemistry]****Calcipotriol hydrate**

Nonproprietary name: Japanese description

Calcipotriol hydrate

Chemical name: (5*Z*,7*E*,22*E*,24*S*)-24-Cyclopropyl-9,10-secochola-5,7,10(19),22-tetraene-1 $\alpha$ ,3 $\beta$ ,24-triol monohydrate

Structure formula:

Molecular formula:  $C_{27}H_{40}O_3 \cdot H_2O$

Molecular weight: 430.62

Description: White crystalline powder.

Freely soluble in methanol, in ethanol (95) and in 2-propanol. Soluble in propylene glycol. Sparingly soluble in ethyl acetate, in dichloromethane and in chloroform. Practically insoluble in liquid paraffin and in water (0.1% disodium hydrogen phosphate solution).

[figure not shown]
**Betamethasone dipropionate**

Nonproprietary name: Japanese description (JP)

Betamethasone dipropionate

Chemical name: 9-Fluoro-11 $\beta$ ,17,21-trihydroxy-16 $\beta$ -methylpregna-1,4-diene-3,20-dione 17,21-dipropionate

Structure formula:

Molecular formula: C28H37FO7

Molecular weight: 504.59

Description: The product is a white to pale yellow crystalline powder without odor.

It is freely soluble in acetone, 1,4-dioxane and chloroform, soluble in methanol, sparingly soluble in ethanol (95), slightly soluble in ether and practically insoluble in water and hexane.

It gradually changes under light.

### [Package]

15g×1, 15g×10, 30g×1

## 15 Appendix 3: Definitions of Adverse Events and Serious Adverse Events

### 15.1 Adverse Event Definition

*An AE is defined as any untoward medical occurrence in a patient or clinical investigation subject administered a pharmaceutical product and which does not necessarily have a causal relationship with this treatment. An AE can therefore be any unfavourable and unintended sign (including an abnormal laboratory finding), symptom, or disease temporally associated with the use of a medicinal (investigational) product, whether or not related to the medicinal (investigational) product. (ICH Harmonized Tripartite Guideline for Good Clinical Practice, E6 (R1)).*

This definition includes:

- Accidental injuries.
- Events related to trial procedures.
- Reasons for any unfavourable and unplanned change in medication (drug and/or dose).
- Clinically significant worsening of pre-existing conditions.
- Reasons for admission to hospital or surgical procedures unless these were planned before the subject consented to trial participation.
- AEs commonly observed and AEs anticipated based on the pharmacological effect of the IMP.
- Any laboratory abnormality assessed as clinically significant by the investigator (see Section 8.6).

### 15.2 Serious Adverse Event Definition

A SAE is any untoward medical occurrence that

- results in death
- is life-threatening
- requires inpatient hospitalisation or prolongation of existing hospitalisation. Planned hospitalisation or planned prolonged hospitalisation do not fulfill the criteria for being an SAE but should be documented in the subject's medical record.
- results in persistent or significant disability/incapacity

- is a congenital anomaly/birth defect

or

- is a medically important condition. Events that may not be immediately life-threatening or result in death or hospitalisation but may jeopardise the subject or may require intervention to prevent one of the other outcomes listed in the definition above. Examples are intensive treatment in an emergency room or at home for allergic bronchospasm, blood dyscrasias and convulsions that do not result in hospitalization, development of drug dependency or drug abuse.

## 16 Appendix 4: Classification of Adverse Events

### 16.1 Severity

The *severity* of the AE should be described in terms of mild, moderate or severe according to the (sub)investigator's clinical judgement.

Mild	An AE that is usually transient and may require only minimal treatment or therapeutic intervention. The event does not generally interfere with usual activities of daily living.
Moderate	An AE that is usually alleviated with additional specific therapeutic intervention. The event interferes with usual activities of daily living, causing discomfort but poses no significant or permanent risk of harm to the subject.
Severe	An AE that interrupts usual activities of daily living, or significantly affects clinical status, or may require intensive therapeutic intervention.

If the severity of an AE worsens, a new AE should be recorded.

### 16.2 Causality

The *causal relation* of the AE to the use of the IMP should be described in terms of probable, possible or not related according to the investigator's clinical judgement. The categories are defined below.

Probably related	
Follows a reasonable temporal sequence from administration of the IMP.
 
Could not be reasonably explained by the subject's clinical state, environmental or toxic factors or other therapies administered to the subject.
 
Follows a known pattern of response to the IMP.
 
Disappears or decreases on cessation or reduction in dose of the IMP.
 
Reappears or worsens upon re-challenge.

Possibly related	
Follows a reasonable temporal sequence from the administration of the IMP.
 
Could also be reasonably explained by the subject's clinical state, environmental or toxic factors or other therapies administered to the subject.
 
Follows a known pattern of response to the IMP.

Not related	
Does not follow a reasonable temporal sequence from administration of the IMP.
 
Is better explained by other factors like the subject’s clinical state, environmental or toxic factors or other therapies administered to the subject.
 
Does not reappear or worsen upon re-challenge.
 
Does not follow a known pattern of response to the IMP.

-------------	---

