### 3.2 Experience with Investigational Medicinal Product

In October 2015, LEO 90100 foam was approved in the US as the first country for the topical treatment of plaque psoriasis in patients 18 years of age and older. Overall, the product has been approved in 36 countries, hereof the majority in EU. The foam was launched in US and EU in 2016.

LEO 90100 foam contains the same fixed combination of calcipotriol hydrate 52.2 µg/g (equivalent to 50.0 µg/g calcipotriol) plus betamethasone dipropionate 0.643 mg/g as in the ointment and gel formulations that have been marketed for treatment of psoriasis vulgaris for years. Moreover, both active substances (and the combination thereof) are well established topical treatments for psoriasis.

The safety profile from the marketed combination products (ointment, gel and foam) is based on more than 21,000 subjects involved in LEO Pharma A/S sponsored clinical trials as well as extensive postmarketing experience.

For the ointment and gel formulations, various skin reactions have been reported. The following common and uncommon adverse drug reactions (ADRs) have been reported: pruritus, skin exfoliation, folliculitis, skin infection, skin atrophy, exacerbation of psoriasis,

dermatitis, erythema, rash, purpura or ecchymosis, skin burning sensation, skin irritation, application site pigmentation changes, application site pain, eye irritation, acne and dry skin.

The most frequently reported adverse events (AEs) related to LEO 90100 foam in trials conducted outside Japan were application site reactions. Also, the following uncommon ADRs have been reported: folliculitis, hypersensitivity, hypercalcaemia, skin hypopigmentation, rebound effect, application site pruritus and application site irritation (Investigator's Brochure section 4.8).

The toxicological profiles of calcipotriol and betamethasone dipropionate are well characterised and as expected for the respective drug classes (i.e. vitamin D3 analogue and corticosteroid).

For Dovobet® ointment, no differences in the safety profile have been observed in Japan during the clinical development programme and postmarketing surveillance compared to overseas.

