#### **9.4.2 LEO Pharma Reporting Responsibilities**

Global Safety, LEO Pharma A/S is responsible for assessing whether or not a SAE is expected. The relevant reference document for those randomised to LEO 90100 foam is the current version of the Investigator's Brochure for LEO 90100 foam. For those randomised to Dovobet® ointment, the relevant reference document is the Japanese package insert for Dovobet® ointment.

Global Safety, LEO Pharma A/S and LEO Pharma K.K. (collectively called as 'LEO Pharma') will notify the regulatory authorities and concerned investigators of SAEs according to the current applicable legislation for the concerned country.

The IRB(s) will be notified of SAEs according to the current applicable legislation for the concerned country. For Japanese sites, the investigator and LEO Pharma K.K. will be notified of the IRB review outcome by the director of the trial site.

All SAEs which are assessed as causally related to the IMP(s) by either the investigator or LEO Pharma A/S, and which are not expected (Suspected, Unexpected Serious Adverse Reactions (SUSARs)) are subject to expedited reporting to regulatory authorities and IRB(s) according to the current applicable legislation in the concerned country. Investigators will be notified of these on an ongoing basis. In addition, in Japan all SAEs which are assessed as causally related to the IMP(s) by either the investigator or LEO Pharma A/S and are subject to expedited reporting in Japan, will be reported to regulatory authorities, IRB(s) and investigators according to the current applicable legislation in Japan.

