6.7.2 Adverse Events

AEs will be analysed as described in the CTP (section 11.3.8.1), with the following additions and clarifications.

Three tables will be produced counting AEs by each causal relationship; not related, possibly related and probably related, respectively.

If different categories of causal relationship were observed for the same SOC and preferred term in one subject, count as one event for each causal relationship.

In addition, three causal relationships will be divided into two categories; "not related" and "related" (possibly related and probably related), and a table for "related" events will be presented. If several events are observed for the same SOC and preferred term in one subject, count as one event for the greatest causality.

Separate tables for "lesional/perilesional" and "distant" cutaneous AEs will also be produced.

Adverse drug reactions are defined as adverse event that is related to trial medication:

Adverse event that is related to trial medication are those classified as the probable or possible relationship to trial medication.

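### Section 16.2 ties both related categories to a known pattern of response, so a new reaction fits neither and may be coded not related

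*Protocol*

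**What the plan says.** Protocol Appendix 4, section 16.2, has three causality categories. The relation "should be described in terms of probable, possible or not related according to the investigator's clinical judgement", and the text then introduces the entries that follow as definitions of those categories. It does not say whether all the features in an entry must be met, or only some.

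- *Probably related* and *possibly related* both include "Follows a known pattern of response to the IMP".
- *Not related* lists the negation of that line. It also lists implausible timing, no recurrence on re-challenge, and one feature on alternative causes: "Is better explained by other factors like the subject’s clinical state, environmental or toxic factors or other therapies administered to the subject".

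Protocol 9.4.2 covers SAEs that are judged causally related by either the investigator or the sponsor "and which are not expected (Suspected, Unexpected Serious Adverse Reactions (SUSARs)) are subject to expedited reporting". The Investigator's Brochure (foam) and the Japanese package insert (ointment) are named there as references for the sponsor's decision on whether an SAE is expected.

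On the analysis side, Protocol 11.3.8.1 counts as related every AE that the investigator has not recorded as *not related*. SAP 6.7.2 states the rule positively: "Adverse event that is related to trial medication are those classified as the probable or possible relationship to trial medication".

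**The concern.** Causality categories should let an investigator record suspicion of a reaction that nobody has described before. Here familiarity is written into both related categories, and unfamiliarity is named only under *not related*. An investigator who follows the text closely is steered towards *not related* for exactly the events that a new formulation's trial should be able to flag.

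Comparing safety is the trial's only secondary objective (Protocol 4.2). The one completed foam trial in Japanese subjects was a single-application study in 20 healthy men (Protocol 3.2). The related-AE and ADR tables, and the decision to follow a non-serious event after the last visit, all depend on this coding.

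**Working it through.** **1. Test two new reactions against the entries in 16.2.** Both have plausible timing and no known pattern. Event A has no other explanation. Event B could also be explained otherwise, but not better.

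| Category | Event A | Event B |
|---|---|---|
| *Probably related* | Timing met; absence of another explanation met; known pattern **fails** | Timing met; absence of another explanation **fails**; known pattern **fails** |
| *Possibly related* | Timing met; possible other explanation **fails**; known pattern **fails** | Timing met; possible other explanation met; known pattern **fails** |
| *Not related* | Implausible timing fails; better explanation fails; unknown pattern **met** | Implausible timing fails; better explanation fails; unknown pattern **met** |

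Read strictly, neither event fits any category in full. Event B misses *possibly related* on the pattern line alone. There is no fourth option, such as not assessable, so one of the three must be chosen. Only *not related* mentions an unknown pattern.

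**2. Compare with 9.4.2.** A SUSAR must be related and not expected. If relatedness presupposes a known pattern, few events could be both. Section 9.4.2 assumes that an unexpected reaction can be related; a strict 16.2 makes that hard to record.

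**3. Trace what depends on the coding.**

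- Affected: SAP Tables 202 and 208–211 and Listing 2.9.2. Events would move into Table 208 (not related) and out of Tables 209–211.
- Affected: follow-up of non-serious AEs after the last visit, which is limited to possible or probable relationship (Protocol 6.1, 9.5; footnote d in 8.1).
- Not affected: the safety endpoint, which is the number of all AEs (Protocol 5.2), and the all-AE tables (SAP Tables 203–207).
- Not affected: SAE reporting within 24 hours (Protocol 9.4.1) and SAE follow-up to final outcome (Protocol 9.5), both of which apply whatever the causality.

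**4. Scale.** The plan has no figure that depends on the causality definition. The only Japanese ADR rate in the documents is in the package insert (Protocol Appendix 2), for ointment and gel together.

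- Terms listed: 5 + 2 + 2 + 8 × 1 = 17. Rate: 17/445 = 3.82%, which matches the stated 3.8%.
- Assume that this rate applies to an arm here. With 90 randomised: 90 × 17/445 = 3.44 subjects. With 80 completing (Protocol 6.2): 80 × 17/445 = 3.06.
- If a share *s* of true reactions were new and coded *not related*, the loss at n = 90 is 3.44 × *s*: 0.34 for *s* = 10%, 0.86 for 25%, 1.72 for 50%, 3.44 for 100%.

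The documents give no value for *s*. These shares only illustrate that the count runs from zero to the few related cases expected.

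**The case against.** The best defence is that 16.2 is guidance. It appeals to clinical judgement and has no rule that every feature must be met. *Probably related* also lists recurrence on re-challenge, yet the visit schedule (Protocol 8.1) has no re-challenge, so a strict reading would leave *probably related* almost empty. Protocol 11.3.8.1 counts anything not positively coded *not related* as related. All AEs are tabulated regardless of causality, and for SAEs the sponsor gives a second causality opinion.

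Much of this stands, and it limits the consequence. It does not remove the defect. The entries are presented as definitions, and sites could apply them differently. The 11.3.8.1 rule does not help once the investigator has chosen *not related*, which is where the text points. The sponsor's second opinion in 9.4.2 covers SAEs only, so for non-serious AEs the investigator's call is the only one described.

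A reader might go further and infer that the known pattern differs by arm, so that related AEs are under-counted for the foam. The short foam list in Protocol 3.2 ("Also, the following uncommon ADRs have been reported: folliculitis, hypersensitivity, hypercalcaemia, skin hypopigmentation, rebound effect, application site pruritus and application site irritation") against the full ointment insert ("Those adverse drug reactions were folliculitis in 5 patients, anaemia and glucose urine present in 2 patients each") invites this. The documents do not support it:

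- Section 16.2 attaches no list of reactions. The arm-specific references in 9.4.2 serve expectedness, not causality.
- The foam list is a summary that points to the Investigator's Brochure, which is not available here. Setting a summary against a full label is not like for like.
- Nine of the insert's 17 ADRs have no obvious match in the foam list. Seven of those nine (anaemia 2, glucose in urine 2, leukocytosis, peripheral oedema, abnormal hepatic function) are also missing from the ointment and gel list in 3.2. The other two, herpes simplex and contusion, arguably fall under that list's skin infection and purpura or ecchymosis.
- The products share active ingredients and concentrations, and a similar safety profile is expected (Protocol 3.4). With open allocation, attribution could as easily lean towards the newer product.

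**Conclusion.** The point holds as a weakness in the definition. As written, 16.2 gives a new reaction no related category and names its unfamiliarity only under *not related*, which is inconsistent with the SUSAR concept in 9.4.2. The possible result is fewer related AEs and ADRs in the tables and no 14-day follow-up for some non-serious events.

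This rests on investigators reading the entries as definitions, which the wording invites but does not compel. No size can be derived. At the ointment and gel rate, only about three subjects per arm would have a related event at all. A difference between arms, its direction, and an under-count specific to the foam are not shown. This is a cheap improvement, not a threat to the trial's safety conclusions.

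**What to change.** In section 16.2, state that a known pattern of response supports relatedness but is not required for it, and that an unknown pattern alone does not make an event *not related*. Deleting the known-pattern line from *possibly related* is an alternative to the first statement, with the second statement still added. Deletion rescues event B. Event A, read strictly, would still miss *possibly related* because it has no other explanation, and *probably related* because of the pattern line. The explicit statement is therefore the fuller repair.

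Keep the Investigator's Brochure and package insert in 9.4.2 for expectedness only. No change to the SAP tables is needed.

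The cost is a sentence or two in Appendix 4 and a mention in site training, with slightly more *possibly related* AEs and 14-day follow-up visits in both arms.
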